## 6. Study Design

PRESERVE-Mitral is a prospective non-randomized non-interventional post-market registry. A total of 200 patients who are eligible and who are intended to be implanted with a Profile 3D™ or CG Future® Annuloplasty system in the surgical repair procedure will be included in the study.

The subjects will be evaluated at discharge for evaluation of procedural success and subsequently followed up as per standard-of-care at the site from 3-6 months (90 days to 210 days) post procedure and at 12 months (365 days +/- 30 days) post procedure for assessment of longer term outcome at which time subjects will also exit the study. Echo images will be evaluated pre-implant, intra-op, discharge and during follow ups, according to the standard routine in the center.

Patients eligible for mitral valve repair and compliant with the enrollment criteria will be considered by the investigator for inclusion in the study.

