## 4.2. Purpose

There is limited local evidence on mitral repair products in South Asia and a prospective post-market registry will provide real world data on clinical outcomes.

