### 6.1. Duration

The enrollment period is anticipated to take about 20 months. The study is expected to start enrolling in July 2017. With a maximum follow-up period of 12 months, the study is expected to last 32 months after the first patient enrollment. It is expected that an additional 4 months would be required for data analysis, and preparation of the publication. This study will be conducted in 10 centers in India, Nepal

and Bangladesh. Each center can include a maximum of 40 subjects in the study, which is 20% of the overall enrollment for the study. There is no minimum enrollment per site applicable for this study.

A site may be selected for participation in the registry if the site complies with the following requirements:

- Sites are expected to adhere to Indian GCP and other local regulations as applicable.
- The site will appoint a Principal Investigator at the physician-in-charge level or above with appropriate experience and qualifications to oversee investigational procedures.
- The PI and other investigators have knowledge and experience in mitral valve repair, e.g. implanting the Profile 3D or CG Future Annuloplasty systems.
- The site has the necessary facilities to conduct the registry (for example echocardiography).
- The site applies a 3-6 month and 12 month follow up as standard practice of care for these patients.
- Site is willing to comply with all requirements of the regulatory agency, Ethics Committees, or Institutional Review Boards, and the CIP.

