# 8. Selection of Subjects

## 8.1. Study Population

The patient population includes all patients suffering from mitral valve disease, indicated for a mitral valve repair procedure, either as a stand-alone procedure or concomitant to another procedure (for example, coronary artery bypass grafting, tricuspid valve repair, treatment of atrial fibrillation, etc. but excluding patients undergoing aortic valve replacement) and for which the surgeon considers the implantation of a Profile 3D™ or CG Future® annuloplasty system most appropriate to reconstruct the regurgitant valve.

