## 9.2. Subject Screening

Patients indicated for mitral repair procedure will be considered for enrollment in this study, and screened based on inclusion/exclusion criteria mentioned in Section 8. Site will maintain a Screening Log to maintain screening information.

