### **13.4. Sample Size Determination**

The sample size of 200 subjects who are eligible and intended to be implanted with a Profile 3D™ or CG Future® Annuloplasty system in the surgical repair procedure is adequate and appropriate for the evaluation of local evidence and obtaining real world data on clinical outcomes following implantation of these two products. This sample size was not statistically derived as this is not a hypothesis driven study.

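### The CIP does not require consecutive invitation of eligible patients, and the SAP does not report those screened or eligible but not enrolled

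*Combined protocol and SAP*

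**What the plan says.** **Entry to the registry.** CIP 6 states: "Patients eligible for mitral valve repair and compliant with the enrollment criteria will be considered by the investigator for inclusion in the study". CIP 9.2 is similar: "Patients indicated for mitral repair procedure will be considered for enrollment in this study, and screened based on inclusion/exclusion criteria mentioned in Section 8". Under CIP 8.2 and SAP 5.2.2 a subject counts as enrolled on signing the consent form.

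**Target population.** CIP 8.1, repeated in SAP 5.2.1, opens: "The patient population includes all patients suffering from mitral valve disease, indicated for a mitral valve repair procedure". It narrows this to patients "for which the surgeon considers the implantation of a Profile 3D™ or CG Future® annuloplasty system most appropriate to reconstruct the regurgitant valve", and leaves out those having concomitant aortic valve replacement.

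**Records and reporting.** CIP 9.2 says: "Site will maintain a Screening Log to maintain screening information". It does not list the log's fields. The log is not named among the site records in CIP 15.7, and neither document plans to report it. SAP 7.1.1 summarises disposition from enrolled subjects onward. SAP 7.6 tabulates baseline data for the Enrolled and Successfully Implanted sets.

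**Size and aim.** CIP 13.4 says of the 200 subjects: "This sample size was not statistically derived as this is not a hypothesis driven study". CIP 6.1 says: "Each center can include a maximum of 40 subjects in the study, which is 20% of the overall enrollment for the study". There is no site minimum. CIP 4.2 gives the purpose: "a prospective post-market registry will provide real world data on clinical outcomes".

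**The concern.** The registry has no comparator and no hypothesis test. Its two primary results, 12-month all-cause mortality and improvement in MR grade, are useful to the extent that the 200 subjects represent the patients who receive these devices at the participating centres. The sponsor makes that claim itself. CIP 4.1 argues that Western evidence may not describe South Asian patients, and SAP 7.12 says the chosen cohorts will cover the populations of interest, having named patients considered eligible for repair as the group to be characterised.

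The plan does not say how subjects are drawn from the eligible patients, and it produces no denominator. A reader of the final report could not tell whether 200 subjects came from 210 eligible patients or from 600. No outcomes are collected on patients who are not enrolled, so any resulting bias could not be corrected afterwards. The planned confidence intervals cover sampling error only.

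**Working it through.** **Is there a sampling rule elsewhere?** I looked where one would normally stand.

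- Eligibility criteria (CIP 8.3-8.4, SAP 5.2.3-5.2.4): none.
- Site requirements (CIP 6.1): a cap and no minimum, but no rule on the order or completeness of invitation.
- Consent (CIP 9.4): how consent is taken, not who must be approached.
- Deviations (CIP 9.10): the listed examples, which are not exhaustive, do not include passing over an eligible patient.
- CIP 8.1 and SAP 5.2.1: these define the target population and do not say how subjects are drawn from it.

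**The plan's own figures.** Cap: 40/200 = 20%, as stated. Five centres at the cap could fill the study (200/40 = 5). Average recruitment over 10 centres and about 20 months is 200/10/20 = 1.0 subject per centre per month. The documents give no eligible caseload per centre, so the enrolled share of eligible patients cannot be computed.

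**Illustration for mortality (all inputs assumed).** 200 of 300 eligible patients are enrolled. Mortality at 12 months is 5% in enrolled patients and 8% or 12% in the other 100.

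- At 8%: (200 × 5% + 100 × 8%)/300 = 18/300 = 6.0%, a gap of 1.0 point.
- At 12%: (200 × 5% + 100 × 12%)/300 = 22/300 = 7.3%, a gap of 2.3 points.

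For comparison, the exact (Clopper-Pearson) 95% interval at 10/200 is 2.4-9.0%. This stands in for the planned Kaplan-Meier interval and assumes complete follow-up of all 200.

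- Average half-width: (9.0 − 2.4)/2 = 3.3 points. The gap is 1.0/3.3 = 30% to 2.3/3.3 = 70% of it.
- Upper arm: 9.0 − 5.0 = 4.0 points. The gap is 1.0/4.0 = 25% to 2.3/4.0 = 58% of it.
- Both all-eligible rates lie inside the interval.

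**Sensitivity to the assumptions.** Let f be the enrolled share, p the rate in enrolled patients and k the risk ratio of non-enrolled to enrolled patients. The all-eligible rate is p × [f + (1 − f) × k]. With p = 5%:

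| f | k | All-eligible mortality |
|---|---|---|
| any | 1 | 5.0% |
| 0.9 | 2 | 5.5% |
| 0.5 | 2 | 7.5% |
| 0.5 | 3 | 10.0% |

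Of these, only the last falls outside 2.4-9.0%.

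**MR improvement (assumed).** With 90% improved in enrolled patients (180/200, exact interval 85.0-93.8%) and 70% in non-enrolled patients, the all-eligible figure f × 90% + (1 − f) × 70% is 88.0% at f = 0.9, 85.0% at f = 0.75 and 80.0% at f = 0.5.

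**The case against.** The strongest reply is that the text does not give investigators leave to omit anyone. Read plainly, CIP 6 and 9.2 have every patient indicated for repair considered, with the published criteria as the only stated filter. That stands. A reader might infer an express discretion to choose among eligible patients, but the documents do not grant one; they are silent. Silence still leaves selection possible.

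A reader might also infer that selection would leave no trace. It would leave some. SAP 7.9.3 reports NYHA class, heart failure symptoms, previous cardiovascular surgery, risk factors, level of regurgitation and type of mitral valve deficiency. Aetiology and the NYHA III/IV share could be set against the Indian series in CIP Table 2. The 40-subject cap limits any one centre's influence, and consent by a legally authorised representative is allowed. These safeguards help, but they do not supply a count of eligible patients who were not enrolled or the reasons.

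Finally, this is a descriptive registry with no pass/fail criteria, and the absence of a consecutive rule contradicts nothing else in the plan. That is fair, and it makes this a design weakness rather than an inconsistency. The surgeon's choice of device and the consent requirement are normal in a device registry and are not at issue.

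**Conclusion.** The point holds as a gap in sampling and reporting. The plan neither limits selective inclusion of eligible patients nor lets a reader judge it beyond the baseline case mix. That matters for a study whose worth rests on being representative.

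Two stronger conclusions are not supported. The documents do not show that selection occurs, and they do not show that it would lower mortality or raise MR improvement. That direction follows only if those passed over are at higher risk. The size is also unknown. The 1.0-2.3 point gap rests entirely on the assumed 200 of 300 and the assumed mortality rates. On those inputs it is smaller than the sampling uncertainty, and only more extreme inputs take the all-eligible rate outside the reported interval. No sample-size or error-rate figure in the plan changes.

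**What to change.** - **CIP 6 and 9.2:** require each site to invite consecutive eligible patients planned for Profile 3D or CG Future repair until its cap is reached, and to record in the existing Screening Log the reason for each non-enrolment.
- **SAP 7.1.1:** report the numbers screened, eligible, invited and consented, overall and by centre, ahead of the disposition categories already listed.
- **If consecutive invitation is not feasible at a centre:** still report that centre's log counts and state the limitation in the clinical study report.

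The cost is a little site time to complete the log, plus a CIP amendment. Under CIP 15.6 a significant amendment needs a justification and EC/IRB approval, here across 10 centres in three countries. The SAP change is lighter, but the counts depend on the log recording them. No visit, test or treatment is added, so the study remains non-interventional.

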### 6.1. Duration

The enrollment period is anticipated to take about 20 months. The study is expected to start enrolling in July 2017. With a maximum follow-up period of 12 months, the study is expected to last 32 months after the first patient enrollment. It is expected that an additional 4 months would be required for data analysis, and preparation of the publication. This study will be conducted in 10 centers in India, Nepal

and Bangladesh. Each center can include a maximum of 40 subjects in the study, which is 20% of the overall enrollment for the study. There is no minimum enrollment per site applicable for this study.

A site may be selected for participation in the registry if the site complies with the following requirements:

- Sites are expected to adhere to Indian GCP and other local regulations as applicable.
- The site will appoint a Principal Investigator at the physician-in-charge level or above with appropriate experience and qualifications to oversee investigational procedures.
- The PI and other investigators have knowledge and experience in mitral valve repair, e.g. implanting the Profile 3D or CG Future Annuloplasty systems.
- The site has the necessary facilities to conduct the registry (for example echocardiography).
- The site applies a 3-6 month and 12 month follow up as standard practice of care for these patients.
- Site is willing to comply with all requirements of the regulatory agency, Ethics Committees, or Institutional Review Boards, and the CIP.

## 6.2. Rationale

This study is a post-market registry, studying products that are already in the markets being studied. The study is designed to be observational, following the standard of care at each centre, in order to obtain real world data on the use of the products. The time period of the first follow up is kept flexible, in accordance with the variation in practice at different centres and in order to maximize compliance. The second follow up (12 month) is a standard timepoint for evaluation of longer term outcomes at all centres. All data collected in the study are as per the centre's standard practice, and no interventional procedure will be added in the study.

## 7. Product Description

### 7.1. General

The Medtronic Profile 3D™ Annuloplasty Ring (Figure 1), Model 680R, consists of a titanium core overmolded with silicone and covered with polyester fabric. The ring must be implanted in the mitral position. The ring is marked at three points by colored sutures; two markers correspond to the trigons of the mitral valve, and one identifies the midpoint of the device. The device size is identified by the inside diameter of the ring at its widest point. The titanium core enables radiographic visualization of the device. Non-clinical testing has demonstrated that the Profile 3D™ Ring is compatible with Magnetic Resonance Imaging (MRI) under normal Magnetic Resonance mode (additional information is provided in Appendix L.1).

Figure 1: Profile 3D™ Annuloplasty Ring

The indications for use are to reconstruct and/or remodel the pathological mitral valve. Valvular insufficiency and/or stenosis may be corrected by appropriate repair and annular remodeling. The Profile 3D product is contraindicated for use with highly calcified valves or in retracted valves with severely reduced leaflet mobility. It is also contraindicated for patients suffering from active bacterial endocarditis.

The Medtronic Profile 3D™ Annuloplasty Ring is commercially released (CE-mark since 2008) and in this study, the Profile 3D ring will be applied only within the indications for use. At the time the protocol was finalized, the Medtronic Profile 3D™ Annuloplasty Ring was also approved in the additional geographies (Nepal) in which the study will be conducted. The technical aspects for the Profile 3D Annuloplasty Ring – Model 680R – are provided in Appendix L.1.

The Medtronic Accessories, 768S Profile 3D™ Sizer Set including 9 Profile 3D™ sizers 24-40 mm, are used to identify the size of the ring. In addition, the Annuloplasty Handle Accessories (7686 Annuloplasty Handle (216 mm length) and/or 7686XL Annuloplasty Handle (373 mm length)) are used to be able to implant the profile ring. The T76880 Profile 3D™ Accessory Tray serves to organize and store the various accessories when not in use and may be used to hold the accessories during sterilization. All accessories are also commercially available in the countries/geographies in which the study will take place.

Figure 2: The Medtronic CG Future® Annuloplasty System (Ring and Band)

The Medtronic CG Future® Annuloplasty Ring Model 638R and the Medtronic CG Future® Annuloplasty Band Model 638B (hereafter referred to as CG Future® Annuloplasty Ring/Band) for mitral valve repair are designed to predictably remodel the annulus to maintain apposition of the anterior and posterior leaflets. Correct annuloplasty ring/band sizing is an important element to achieve a successful repair.

The CG Future® COMPOSITE Ring is the first composite ring to offer posterior remodeling while maintaining anterior flexibility. A flexible anterior segment seamlessly connects to the ring's semi-rigid posterior, providing the support needed to dynamically remodel the annulus, thereby allowing physiologic movement throughout the cardiac cycle. It has an unique eyelet design for easy anchoring to the trigones. Semi-rigid design offers enough flexibility to allow movement of the mitral annulus during the cardiac cycle. The band is ideal for small incisions and minimally invasive procedures where visibility and access to the anterior portion of the mitral annulus may be limited.

The CG Future® Ring is available in eight sizes ranging from 24 mm to 38 mm.

The CG Future® Band is available in seven sizes ranging from 26 mm to 38 mm.

## 7.2. Manufacturer

The products are manufactured by Medtronic, PLC.

## 7.3. Packaging

The PROFILE 3D™ and CG Future® annuloplasty systems are commercially available. Refer to IFU for packaging and storage information.

## 7.4. Intended Population

The PROFILE 3D™ and CG Future® systems are indicated for the reconstruction and/or remodeling of pathological mitral valves. Valvular insufficiency and/or stenosis may be corrected by appropriate repair and annular remodeling.

### CONTRAINdicATIONS

- Heavily calcified valves.
- Valvular retraction with severely reduced mobility.
- Active bacterial endocarditis.

## 7.5. Equipment

All equipment for collecting data will be as available at the site.

## 7.6. Product Use

The product should be used as per the Directions For Use outlined in the Instructions For Use insert that comes packaged with the products (Appendix L.1.).

## 7.7. Product Training Requirements

This is a post-market registry, hence there is no requirement for specific product training.

## 7.8. Product Receipt and Tracking

All devices being used in this study are commercially available in the countries/geographies in which the study will be conducted. Therefore, the devices will be used off the shelf. The products are provided to the hospital with the appropriate language labeling. In this study, the Profile 3D and CG Future products will be applied only within the indications for use. Existing procedures for commercial product regarding distribution, shipment, receipt and tracking of these devices will be followed. Additional device traceability is not applicable for this study.

## 7.9. Product Storage

All devices being used in this study are commercially available in the selected countries/geographies in which this study will take place.

Refer to the Instructions for Use for storage of the study device (Appendix L.1.).

## 7.10. Product Return

The study will follow the commercial process for explanted device to be properly retrieved, packaged and shipped to sponsor, which is the same as the process followed for the device in the market.

## 7.11. Product Accountability

Except documentation of serial numbers and model numbers of devices being used in this study, there are no device tracking requirements. The documentation of these numbers needs to be recorded on the eCRF.

# 8. Selection of Subjects

## 8.1. Study Population

The patient population includes all patients suffering from mitral valve disease, indicated for a mitral valve repair procedure, either as a stand-alone procedure or concomitant to another procedure (for example, coronary artery bypass grafting, tricuspid valve repair, treatment of atrial fibrillation, etc. but excluding patients undergoing aortic valve replacement) and for which the surgeon considers the implantation of a Profile 3D™ or CG Future® annuloplasty system most appropriate to reconstruct the regurgitant valve.

## 8.2. Subject Enrollment

A subject is considered enrolled in this study at the time at which he/she signed the Patient Informed Consent Form.

The investigator will maintain a log of all subjects enrolled in the study assigning an identification code linked to their names, alternative subject identification or contact information.

## 8.3. Inclusion Criteria

1. Patients with valvular insufficiency and/or stenosis and indicated for the reconstruction and/or remodeling of pathological mitral valves with Profile 3D™ and CG Future™ annuloplasty systems
2. Indications and contraindications provided in the product Instructions for Use
3. Subject is 18 years of age or older
4. The patient or his/her Legally Authorized Representative (LAR) has been informed about the nature of the registry and the patient informed consent for study participation has been obtained prior to performing any study-related procedures from the subject or Legally Authorized Representative, as per applicable local requirements

## 8.4. Exclusion Criteria

1. Contraindications as per IFU:
  - a. Heavily calcified valves
  - b. Valvular retraction with severely reduced mobility
  - c. Active bacterial endocarditis
2. Aortic valve replacement as concomitant procedure
3. Already participating in another clinical study, possibly leading to bias and jeopardizing the scientific appropriate assessment of the study endpoints

## 9. Study Procedures

### 9.1. Schedule of Events

The following table (Table 1) lists the schedule of events for the study for each study related visit.

Table 1: Schedule of Events

Visit	Procedure	Data Collection
Baseline/Pre-Operative (data from most recent assessment)	Enrollment	Consent Eligibility assessment (inclusion/exclusion criteria)
	Patient Data	Patient Demographics

**Medtronic Confidential**

# PRESERVE-Mitral Clinical Investigation Plan

MDT16016SUR002

Version 1.0, dated 10-APR-2017

Page 23 of 58

Medtronic

before planned implant date preferred, not exceeding 60 days)		Pre-Operative Clinical History (cardiac rhythm, previous procedures, symptoms, risk factors, lesion information, etc.) Medications
	Echo	MR Mitral Gradient Leaflet coaptation Aortic and Tricuspid valves HF parameters (LVEF, LVEDD, LAD, etc.)
Implant	Implant Data	Procedure Details Repair Details Concomitant Procedures Sizing Serious Adverse Events including major adverse cardiac or cerebrovascular events (MACCE) as defined in section 11.1
	Echo	Intra-op echo
Discharge (date of discharge or 7 days post procedure, whichever comes first)	Health Assessment	Subject Assessment (Cardiac rhythm, NYHA, etc.) Serious Adverse Events including major adverse cardiac or cerebrovascular events (MACCE) as defined in section 11.1 Medication
	Echo	MR Mitral Gradient Leaflet coaptation Aortic and Tricuspid valves HF parameters (LVEF, LVEDD, LAD, etc.)
3-6 Month Follow Up (data reported from 90 days up to 210 days post procedure, whichever comes later)	Health Assessment	Subject Assessment (Cardiac rhythm, NYHA, etc.) Serious Adverse Events including major adverse cardiac or cerebrovascular events (MACCE) as defined in section 11.1 Medication
	Echo	MR Mitral Gradient Leaflet coaptation

